### **13) Data and Specimen Banking**

N/A

### **14) Data Management**

This study will be a single blinded, randomized, intra-individual comparison study consisting of a total of 12 subjects. A power analysis is not truly applicable because this is a pilot study that utilizes a potential treatment for seborrheic dermatitis that has not been previously investigated. We plan to recruit up to 12 patients.

SASI-F scores and the SebuMeter® measurements will be compared within the treatment group and an intra-individual comparison will be performed by paired statistical testing such as the paired t-test. A p-value of 0.05 or less will be considered significant. All of the assessors will be blinded to the treatment groups. The primary endpoint will be complete clearance of the seborrheic dermatitis as an intra-individual comparison and statistically analyzed with a two-sided paired t-test. All participants will be included in the study on an intent-to-treat basis.

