**4) Objectives**

a) To determine the efficacy of photodynamic therapy (PDT) in the treatment of seborrheic dermatitis.

b) To determine how PDT alters the skin microbiome in subjects with seborrheic dermatitis before and after treatment.

c) To determine how PDT alters sebum secretion rates in subjects with seborrheic dermatitis before and after treatment.

We hypothesize that PDT will be efficacious in the treatment of seborrheic dermatitis.

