This study will be a single blinded, randomized, intra-individual comparison study consisting of a total of 12 subjects. Patients will be randomized by utilizing an online randomizer. A power analysis is not truly applicable because this is a pilot study that utilizes a potential treatment for seborrheic dermatitis that has not been previously investigated. We plan to recruit up to 12 patients. The treatment will consist of split-face comparisons of no application of aminolevulinic acid (ALA) vs ALA application to either half of the face. Prior to ALA application, the face will be swabbed for microbiome analysis. A schematic for the split-face study is shown in Figure 1. After the ALA application, the subjects will incubate with the ALA on their face per the standard PDT protocol used at UC Davis Dermatology clinic for facial PDT treatments. The side of the face being treated will remain the same during all treatments. The investigator applying the ALA to the patient will be aware of which side is receiving treatment and which side is not, but the patient will be blinded. For the placebo, Demo Levulan Kerastick, which contains no active ingredient and is enclosed in same cardboard sleeve and cap, will be applied to the other side of the face to mimic the surface of the ALA application stick.

PROTOCOL TITLE: Pilot study for the use of photodynamic therapy in the treatment of seborrheic dermatitis

After the ALA incubation is completed, the subjects will be exposed to a treatment dose of blue light from a Blu-U unit per UC Davis Dermatology clinic protocol for PDT treatments.

Calibrated facial pictures will be used for blind grading utilizing the SASI-F scoring system.

A flow diagram of the protocol is shown in Figure 2. The topical ALA used for this study will be Levulan® Kerasticks (DUSA Pharmaceuticals, Inc.). Facial sebum production rate will be measured with SebuMeter®. The swabbing for the microbiome will be performed as non-invasive swabbing from the face that will not cause the patient any pain or discomfort. For the blue light treatment, the total light dose to the face will be consistent with the currently used standard facial exposure PDT protocols at UC Davis.

After the third visit, patients have the option of being seen in the regular dermatology clinics. Based on the disease severity, a treatment modality will then be selected and administered for the untreated side of the face.

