## **32) Consent Process**

Written consent will be obtained from patients at the UC Davis outpatient Dermatology clinic in Sacramento. We will be following the SOP: Informed Consent Process for Research. After obtaining consent, there will be a two-week waiting period before initiating treatment so that the patient may begin using only

PROTOCOL TITLE: Pilot study for the use of photodynamic therapy in the treatment of seborrheic dermatitis

Dove soap and stop using any other products to their face. If the patient is using systemic treatment they will have to wait 4 weeks before participating, and if the patient is using topical treatment they will have to wait 2 weeks before participating. Patient will also be provided a moisturizer and sunscreen to use as needed. Patient will be encouraged to use sunscreen following PDT treatments.

Only English-speaking, adult subjects who are not cognitively impaired and are able to consent will be recruited.

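### Section 14 plans two unranked analyses of SASI-F and sebum and lets either count as significant at 0.05; the within-treatment-group one cannot separate an ALA effect from change shared by both halves of the face

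*Combined protocol and SAP*

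**What the plan says.** Section 14 (Data Management) covers SASI-F and the sebum readings in one sentence: they "will be compared within the treatment group and an intra-individual comparison will be performed by paired statistical testing such as the paired t-test". The next sentence sets the threshold: "A p-value of 0.05 or less will be considered significant". The visit, the use of change or final score, and the meaning of the within-group comparison are all left open, and neither analysis is put ahead of the other. The same section states the primary endpoint separately: "The primary endpoint will be complete clearance of the seborrheic dermatitis as an intra-individual comparison and statistically analyzed with a two-sided paired t-test".

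Section 12 (Procedures Involved) uses the same term for the design: "This study will be a single blinded, randomized, intra-individual comparison study consisting of a total of 12 subjects". One half of the face receives ALA, the other a demonstration applicator with no active ingredient. The Figure 1 legend says that the side is randomised. Light follows: "the subjects will be exposed to a treatment dose of blue light from a Blu-U unit". No shielding of the control half is described.

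Section 4 (Objectives) words objective c as "To determine how PDT alters sebum secretion rates in subjects with seborrheic dermatitis before and after treatment", and objective b uses the same before-and-after frame for the microbiome. Neither mentions the control half. Section 11 (Study Endpoints) schedules severity grading, swabs and sebum rates before each treatment and after each follow-up period.

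**The concern.** A comparison within the treatment group is a single-arm comparison. With objectives b and c asking about before and after, and section 11 scheduling measurements at those times, its natural reading is a pre/post test on the ALA half. Such a test attributes to PDT everything that happened to that half over the period.

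Several influences would move both halves together: natural fluctuation of a chronic relapsing condition, carry-over from the washout of earlier treatments (in either direction), and some regression to the mean, because subjects need active disease to enter. The split-face control removes these, but only in the between-half contrast.

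Because either analysis may be called significant at 0.05, a fall in SASI-F or sebum on the ALA half could support a claim of PDT effect even if the control half fell just as much.

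**Working it through.** **Inputs.** N = 12 (sections 7, 12, 14 and 27). Threshold 0.05 (section 14). Section 14 states two-sided testing only for the primary endpoint; it is assumed here for SASI-F and sebum too. The documents give no power, effect size, SD or correlation, so there is no figure of the plan's own to reproduce. The shared shifts and correlations below are assumptions.

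**Step 1: within-group test when ALA has no effect.** Let both halves change by d, in units of the SD of a half-face change score. The paired t statistic on the ALA half then follows a noncentral t distribution with 11 degrees of freedom and noncentrality d × √12. The two-sided critical value is 2.201.

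| Assumed shared change d | Noncentrality d × √12 | Within-group test significant |
|---|---|---|
| 0 | 0 | 5.0% |
| 0.2 | 0.693 | 9.7% |
| 0.3 | 1.039 | 15.8% |
| 0.5 | 1.732 | 35.3% |
| 0.8 | 2.771 | 71.4% |

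**Step 2: between-half test under the same conditions.** For each subject take (ALA post − pre) − (control post − pre). The shared change d cancels. In simulations of 100,000 trials per setting, with correlations of 0.3, 0.5 and 0.8 between the halves' changes, a paired t-test on this difference was significant in 4.9% to 5.2% of trials, whatever the value of d.

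**Step 3: either test may count.** In the same type of simulation, the chance of at least one significant result for one outcome is about 9% at d = 0, 19% to 20% at d = 0.3, 38% at d = 0.5 and 73% at d = 0.8. Planning the controlled test alongside does not protect the conclusion unless the two are ranked.

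**Step 4: how much regression to the mean could contribute alone.** Take a normal score, selection above a cut that removes the mildest fraction q, and test-retest correlation r. With k the standard normal q-quantile, λ = φ(k)/(1 − q) and v = 1 + kλ − λ², the expected change is (1 − r)λ and its SD is √[(1 − r)²v + 1 − r²].

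- q = 0.2 gives λ = 0.350 and v = 0.583. At r = 0.5 the shift is 0.175/0.946 = 0.185 SD and the within-group test is significant in 9.0% of trials; at r = 0.85 it is 0.097 SD and 6.1%.
- q = 0.5 gives λ = 0.798 and v = 0.363. At r = 0.5 the shift is 0.399/0.917 = 0.435 SD and 28.0%; at r = 0.85 it is 0.224 SD and 10.9%.

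Section 12 sets a low entry cut (erythema of at least 1 and at least 5% of the face, on a score with maximum 8), so the smaller figures are the more plausible if few candidates are screened out.

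**The case against.** The strongest reply is that the controlled analysis is already planned. The sentence that mentions the treatment group goes on to an intra-individual comparison, which is the protocol's own term for its split-face design, and the primary endpoint in section 14 is intra-individual too. This stands. A reader might infer that the control half goes unused for SASI-F and sebum; the documents do not support that. What remains is that the uncontrolled test has its own route to significance, and that neither contrast is defined. A before/after test is also paired and within a person, so some ambiguity persists.

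Other parts of the reply also stand:

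- *Before versus after* is an inference. The words are in objectives b and c, not in section 14, and could merely describe when measurements are taken.
- Section 14 specifies no microbiome test, so a faulty one cannot be charged to the plan. Section 12 says "Prior to ALA application, the face will be swabbed for microbiome analysis" without naming a side, but Figures 1 and 2 are not available here and may settle this.
- A reader might blame the new skin regimen for a spurious change. Section 32 has it begin before treatment: "After obtaining consent, there will be a two-week waiting period before initiating treatment so that the patient may begin using only" a single soap. Part of its effect should already be in the pre-treatment value. The baseline visit may be defined in Figure 2.
- Regression to the mean may be small, as step 4 shows, and subjects are not selected on sebum, so for that outcome it is indirect.
- A reader might call a contribution from light a false credit. Light is part of PDT, so it is one only if the question is what ALA adds.
- The rates in step 1 are generic to a paired t-test at n = 12. Nothing in the documents shows that a shared shift would be as large as 0.8 SD.

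**Conclusion.** The point holds in a limited form. The fault is not a missing controlled analysis. It is an uncontrolled test, allowed its own significance claim, beside a controlled one, with neither defined nor ranked. On its most natural reading, the within-group test would be significant in about 16%, 35% or 71% of trials with no ALA effect, for shared changes of 0.3, 0.5 or 0.8 SD, against 5% for the between-half contrast. These rates rest on the assumed shifts, on 12 evaluable subjects and on approximately normal change scores. A shared worsening would bias the within-group test the other way and could hide an effect.

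This should be corrected, although it does not undermine the primary comparison, which section 14 already makes intra-individual.

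**What to change.** In section 14, name one inferential analysis for SASI-F and for sebum: the ALA-half minus control-half difference in change from the pre-treatment value, at a stated visit, by a two-sided paired test. Regressing the follow-up difference between halves on the baseline difference is an acceptable alternative. Report within-half changes descriptively, with confidence intervals and no significance claim.

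Align objectives b and c so that any conclusion about sebum rests on the between-half contrast, and likewise any conclusion about the microbiome if swabs are side-specific. State that readings and swabs are taken separately from each half.

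The cost is wording, plus a second swab per visit if one is not already planned; side-specific sebum readings are already implied by the planned intra-individual comparison. The downside is a narrower question. Since the control half appears to receive light as well, the contrast estimates the effect of ALA added to light, not of PDT against no treatment. The protocol should say so, particularly as section 12 also refers to that half as untreated.

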## **11) Study Endpoints**

The primary endpoint of the study is recruitment of a sufficient number of patients (12) who complete two treatments of photodynamic therapy to the face with grading of the severity of seborrheic dermatitis before each treatment and after each follow-up period.

The secondary endpoints for the study are obtaining swabs for microbiome analysis and facial sebum production rates before each treatment and after each follow-up period.

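### Section 14 does not say whether or how each half-face's pre-treatment value enters the between-side comparison of SASI-F and sebum; a baseline-adjusted paired analysis should be pre-specified.

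*Combined protocol and SAP*

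**What the plan says.** Section 14 (Data Management) describes an "intra-individual comparison study consisting of a total of 12 subjects". Its analysis of SASI-F and sebum has two parts. The between-side part, which matters here, is that "an intra-individual comparison will be performed by paired statistical testing such as the paired t-test". The other part is confined to one arm: "SASI-F scores and the SebuMeter® measurements will be compared within the treatment group". The threshold is given as "A p-value of 0.05 or less will be considered significant". Nothing states which quantity is paired, at which visit, or whether a pre-treatment value is used.

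Section 11 (Study Endpoints) shows that pre-treatment data are collected: "grading of the severity of seborrheic dermatitis before each treatment and after each follow-up period", and "facial sebum production rates before each treatment and after each follow-up period". The caption of Figure 1 says that the two arms are assigned at random to the left or right side. Section 12 (Procedures Involved) defines the SASI-F area index for the whole face. Half-face scoring therefore follows from the split-face design but is not written down.

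**The concern.** Pairing removes what the two halves of a face share. It does not remove a left-right difference that was there before treatment. With 12 randomised pairs such differences will seldom average exactly to zero, and if they persist, part of the imbalance appears in a comparison of final values.

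Three analyses fit the wording of section 14: a paired test on final values, a paired test on changes, and a paired analysis adjusted for baseline. Their precision can differ greatly at this sample size. Because the plan does not choose among them, the choice could also be made after the 12 pairs have been seen.

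**Working it through.** **Inputs from the documents.** There are 12 subjects and the significance level is 0.05 (section 14). Two-sided testing is stated for the complete-clearance endpoint ("statistically analyzed with a two-sided paired t-test") and is assumed here for SASI-F and sebum. The plan gives no effect size, SD or power ("A power analysis is not truly applicable because this is a pilot study"), so it has no figure to reproduce.

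**Assumptions.** The unit is the SD of the within-subject side difference, taken as equal at baseline and follow-up. The correlation r between the baseline and final side differences is not given; the range 0 to 0.7 is shown. The relation is taken as linear.

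**Chance imbalance.** The SE of the mean baseline side difference is 1/√12 = 0.29 SD, so its 95% range is ±1.96/√12 = ±0.57 SD. A final-value comparison is expected to carry a share r of that imbalance. At r = 0.5 and the 95% limit this is 0.5 × 0.57 = 0.28 SD.

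**Variance of each estimate, relative to a final-value paired test (1.00, 11 df), n = 12.**

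- Change scores: 2(1 − r), 11 df.
- Regression of the final side difference on the baseline side difference, with the intercept as the effect: (1 − r²)(1 + 1/(n − 3)) = (1 − r²) × 10/9, 10 df.
- CI width ratio, regression to final value: √[(1 − r²) × 10/9] × 2.228/2.201.

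| r | Variance, adjusted | CI width ratio, adjusted | Variance, change | Detectable difference at 80% power, adjusted (SD) | Detectable difference at 80% power, change (SD) |
|---|---|---|---|---|---|
| 0 | 1.11 | 1.07 | 2.0 | 0.95 | 1.26 |
| 0.3 | 1.01 | 1.02 | 1.4 | 0.90 | 1.05 |
| 0.5 | 0.83 | 0.92 | 1.0 | 0.82 | 0.89 |
| 0.7 | 0.57 | 0.76 | 0.6 | 0.68 | 0.69 |

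The final-value test detects 0.89 SD with 80% power at every r.

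**Break-even points.** On variance, (1 − r²) × 10/9 = 1 gives r = √0.1 ≈ 0.32. On CI width, allowing for the lost degree of freedom, it is about 0.35. Change scores beat final values only when 2(1 − r) < 1, that is r > 0.5. Regression beats change scores when (1 + r) × 10/9 < 2, that is r < 0.8.

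**Simulation (40,000 trials per setting).** With no effect, all three analyses rejected in about 5% of trials (4.8% to 5.2%). At a true difference of 0.889 SD, power at r = 0, 0.3, 0.5 and 0.7 was 76%, 79%, 86% and 95% for regression and 51%, 66%, 80% and 95% for change scores. It was about 80% throughout for final values.

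**Fewer pairs.** With 8 analysable pairs the factor is 1 + 1/5 = 1.2 and the t quantiles are 2.447 (6 df) and 2.365 (7 df). The CI width ratios are about 1.13 (r = 0), 1.08 (r = 0.3) and 0.98 (r = 0.5).

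**The case against.** The strongest reply is that silence is not a decision. A reader might infer that the plan discards the baseline. The text does not support that: the example of a paired t-test leaves the method open, a test on changes would fit it, and the sebum objective in section 4 is framed as before versus after treatment. This stands, and the point is therefore a gap in specification. It does not remove the point, because a before-after test within the treated side leaves the between-side contrast unadjusted, and a change-score test is less precise than final values alone when r is below 0.5.

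A reader might also infer that chance imbalance biases the result. It does not. Sides are randomised, and the 0.28 SD shift lies within the half-width of the unadjusted CI, 2.201/√12 = 0.64 SD. It is part of the variance already counted, not an added harm.

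Nor can it be said outright that precision is lost. The gain depends on r for side differences, which cannot be assumed to match the correlation of raw scores. At low r, or with few pairs, adjustment costs something. Recruitment is up to 12, and section 16 stops data collection for subjects withdrawn without their consent, so fewer than 12 pairs is realistic.

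Two further cautions stand. SASI-F is a bounded product of ordinal grades and an area fraction, so a few asymmetric subjects could set the slope. And this is a pilot, whose stated primary endpoints (recruitment and completion in section 11, complete clearance in section 14) are not affected.

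**Conclusion.** The point holds as a gap with a concrete remedy. The plan has severity and sebum measured before treatment but does not say whether or how those values enter the between-side comparison.

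Under the stated assumptions and 12 pairs, adjustment lowers the variance by about 17% at r = 0.5 and 43% at r = 0.7, is neutral at r = 0.3 and raises the variance by 11% at r = 0. The possible gain is larger than the possible loss, but which of them applies cannot be known from the documents. Across r = 0 to 0.7, regression is also the safer choice against change scores, whose variance is double that of final values at r = 0.

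The conclusion rests on equal variances at the two times, a linear relation and per-half scoring. It concerns precision, and it calls for a change of wording, not of design.

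**What to change.** In section 14:

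1. State that SASI-F and sebum are scored separately for each half of the face at each assessment, with the area index defined for a half.
2. Name the final follow-up visit used for the between-side comparison.
3. Make that comparison a regression of each subject's ALA-minus-control difference at that visit on the same difference before the first treatment. Report the intercept as the treatment effect with its 95% CI.
4. Keep the unadjusted paired test on final values as a sensitivity analysis.

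The cost is plan wording and one degree of freedom. If r is near zero, the CI is up to about 7% wider with 12 pairs and about 13% wider with 8. No new data are needed if the halves are already scored separately, as the design implies. The change does not cover the complete-clearance endpoint.

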## **12) Procedures Involved**

Duration of seborrheic dermatitis, previous treatments for seborrheic dermatitis and patient response to the treatments will be recorded. Facial photography will be done for grading the Seborrhea Area and Severity Index Face (SASI-F). All seborrheic dermatitis patients will be graded using the SASI-F [3]. This score is a composite score as follows: the area index, also known as the relative area of facial involvement, is denoted as a fraction of 1 with the normal hairline defining the boundaries of the face. Erythema and scale are separately scored on a 5-point scale using the definitions used to conduct Psoriasis Area and Severity Index scoring (ie, 0 = none, 1 = slight, 2 = moderate, 3 = striking, and 4 = exceptionally striking).

The scores for erythema and scale are then summed and multiplied by the relative area of facial involvement ratio. The maximal score is 8 whereas no involvement would have a score of 0. The inclusion criteria will be similar to the previous trial that used the SASI-F in their analysis [3]. This study will consist of subjects with an erythema score of at least one with the presence of at an area index of 5% or more.

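### The Section 14 primary endpoint keeps only complete clearance from a graded 0-8 score, so with 12 pairs the primary analysis may well miss a real but incomplete effect

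*Combined protocol and SAP*

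**What the plan says.** Objective (a) in Section 4 is "To determine the efficacy of photodynamic therapy (PDT) in the treatment of seborrheic dermatitis".

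Section 12 grades severity with SASI-F: erythema and scale, each 0 to 4, are added and multiplied by the fraction of the face involved. "The maximal score is 8 whereas no involvement would have a score of 0".

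Section 14 covers the analysis:

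- It plans paired within-subject comparisons of SASI-F and sebum, without calling either primary.
- On the primary it says "The primary endpoint will be complete clearance of the seborrheic dermatitis as an intra-individual comparison", to be "statistically analyzed with a two-sided paired t-test".
- The criterion is "A p-value of 0.05 or less will be considered significant".
- On sample size it says "We plan to recruit up to 12 patients" and "A power analysis is not truly applicable because this is a pilot study".

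No expected clearance rate, effect size or standard deviation is given. Section 11 names a different primary endpoint, a recruitment and completion target.

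**The concern.** Complete clearance records only whether a half-face has reached zero. Take a half that starts with erythema 2 and scale 2 over its whole area, a score of (2 + 2) x 1 = 4.0. Suppose it ends with erythema 1 and scale 0 over a tenth of that area, (1 + 0) x 0.1 = 0.1. If the control half stays at 4.0, the primary comparison scores this subject as no difference, the same as a subject in whom nothing changed.

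With at most 12 pairs there is little information to spare. If PDT improves the disease substantially but seldom clears it, the primary test can fail although the graded data collected from the same subjects show the effect. The reported primary conclusion on efficacy is what is at stake.

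**Working it through.** **Inputs.** From Section 14: at most 12 pairs, two-sided paired t-test, significance at p of 0.05 or less. From Section 12: SASI-F range 0 to 8. Assumed, because the documents give none: clearance rates on each half, and independence of the two halves within a subject. The plan has no power figure to reproduce.

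**Notation.** b = subjects clear on the ALA half only; c = subjects clear on the control half only. All other subjects contribute a difference of 0.

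**Threshold under the planned t-test.** Differences are +1, -1 or 0, so

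mean = (b - c)/12, s² = [(b + c) - (b - c)²/12]/11, t = mean/(s/√12), with 11 df.

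- b = 3, c = 0: mean 0.250, s² = (3 - 0.75)/11 = 0.2045, t = 1.915, p = 0.082.
- b = 4, c = 0: mean 0.333, s² = (4 - 1.333)/11 = 0.2424, t = 2.345, p = 0.039.

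The minimum is 4. With one control-only clearance it is 7 (7 v 1, p = 0.026; 6 v 1, p = 0.054). With two it is 9 (p = 0.027).

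**Threshold under an exact paired (McNemar) test.** With c = 0, p = 2 x 0.5^b.

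- b = 5: p = 0.0625.
- b = 6: p = 0.031.

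The minimum is 6. With one control-only clearance it is 8 (8 v 1, p = 0.039; 7 v 1, p = 0.070). With two it is 10 (p = 0.039).

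**Power.** With clearance rates pA (ALA) and pC (control), and independent halves, P(ALA only) = pA(1 - pC) and P(control only) = pC(1 - pA). Power is the sum of the trinomial probabilities of all (b, c) with b > c and p ≤ 0.05. With pC = 0 this reduces to a binomial tail. For pA = 30% under the t-test it is P(b ≥ 4) = 1 - (0.0138 + 0.0712 + 0.1678 + 0.2397) = 0.507.

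| Assumed clearance, ALA v control | Planned paired t-test | Exact paired test |
|---|---|---|
| 15% v 1% | 8% | under 1% |
| 29% v 1% | 44% | 9% |
| 30% v 0% | 51% | 12% |
| 40% v 0% | 77.5% | 33% |
| 50% v 5% | 73% | 45% |
| 50% v 0% | 93% | 61% |

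With no clearance on the control half, 80% power needs about 41% of ALA halves to clear under the t-test, or about 58% under the exact test.

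**Benchmark for a graded difference.** A two-sided paired t-test with 12 pairs has 80% power at a standardised mean difference of about 0.89 (noncentral t). It does not require any subject to clear. The documents give no standard deviation, so this cannot be converted into SASI-F points or matched to the clearance rates in the table.

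**The case against.** The strongest defence has four parts.

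**The graded comparison is already planned.** A reader might infer that the trial cannot answer objective (a). The documents do not support that: Section 14 already compares SASI-F within subject at the 0.05 level. What is at issue is which planned analysis carries the primary label. That still matters, because a positive SASI-F result would have to be read beside a failed primary.

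**The planned test is less demanding than an exact one.** A reader might infer that at least 6 ALA-only clearances are needed and that the trial would very probably report no efficacy. Six belongs to an exact test the plan does not name; under the planned t-test the minimum is 4. Nor can the t-test be set aside here as plainly too liberal. With equal, independent clearance on both halves at 5%, 10%, 20% and 30%, its two-sided rejection rate is about 0.2%, 1.6%, 4.5% and 5.1%. If half the ALA halves and no control halves clear, its power is 93%. The wording that survives is that the primary may well miss an incomplete effect.

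**This is a pilot, and clearance is easy to interpret.** Both are fair. Low power is openly accepted, and Section 11 also sets a feasibility target as primary. But Section 14 still attaches a two-sided test at 0.05 to clearance, and Section 4 hypothesises efficacy. A small sample is a reason to keep the graded information.

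**Half-face SASI-F is not written down.** This stands. Section 12 defines area against the whole face. The split-face design and the within-subject SASI-F comparison imply scoring by side, but the plan must say so.

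**Conclusion.** The concern holds as a loss of information in the Section 14 primary efficacy endpoint, under either test. It does not show that the trial is unable to assess efficacy.

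Its size depends on how often ALA-treated halves clear completely, which the documents do not address. If clearance is common on the ALA half and absent on the control half, the planned test does well. If it is around 30% or lower, power is about one half or less, falling to about 8% at 15% v 1%. Small amounts of control-side clearance raise the threshold quickly, from 4 to 7 with a single such subject. All the power figures rest on assumed rates, independent halves and a full 12 pairs. The thresholds rest only on the 12 pairs and the named test.

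The change is worth making before any data are analysed, because it costs little and the graded measurement is already part of the plan.

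**What to change.** In Section 14, name as the primary efficacy outcome the within-subject ALA-minus-control difference in SASI-F at the final follow-up, analysed with the two-sided paired t-test already specified. Keep complete clearance as a secondary outcome, reported as paired counts: clear on both halves, ALA only, control only, neither.

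In Section 12, state that SASI-F is scored separately for each half-face, with the area fraction taken relative to that half.

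The cost is protocol wording; no added subjects, visits or procedures are needed. The headline result becomes a difference in score points rather than a statement that disease cleared, which the secondary count still supplies.
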